Instances where the study drug is discontinued include the following: development of a contraindication to metformin as described under the section for exclusion criteria; development of lactic acidosis; diagnosis of diabetes; hospitalization; 48 hours prior to procedures or scans that require contrast medium; or development of B12 deficiency. For those who are hospitalized or receive contrast medium, efforts will be made to recheck kidney function within 48 hours after discharge/procedure and the study drug will be restarted if there is no evidence of renal dysfunction. For tests or procedures that require fasting, study drug will be stopped 24 hours prior to test or procedure, and study drug can be resumed after the participant is allowed to eat again. Compliance to study drug will be tracked and accounted for in analyses.

Study Procedures

All study procedures are research-related.

Exam: Exams for annual visits will occur at OHSU after fasting labwork has been drawn at VAPORHCS. At Screening, baseline and yearly exams, height will be measured in meters using a wall-mounted Harpenden stadiometer, body weight will be measured in kilograms using a balance beam scale, waist and hip circumference measured with a tape measure, and measurements of pulse and blood pressure will be taken.

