The payments are reasonable and commensurate with the expected contributions of the subject. Each annual study visit is 2-3 hours. Baseline and annual visits include a fasting blood draw, height, weight, blood pressure, questionnaires, performance tests, and DXA. The procedures at every 6 month study visits (in between annual visits) are only fasting labs and questionnaires for all participants. For the muscle biopsy substudy, there will be a separate 1-2 hour visit at baseline and an additional 1 hour added to the 6 month visit.

Payments are fair and appropriate and do not constitute (or appear to constitute) undue pressure or influence on, or coercion of, the prospective research subjects to volunteer for or continue participation in the research study.

Statistical considerations

Sample Size and Power

Based on prior observational findings, there was a significant difference (2.2%, p< 0.01) in the percentage change in appendicular lean mass over 3.5 years between metformin-treated and untreated men. The sample size required for 80% Power to detect this difference and reject the null with SD=4% and α =0.05 for an unpaired, 2-sided t-test is 106 study participants (53 in each group). We plan to enroll 300 participants and, of those, randomize 120 (60 in each group) to allow for potential drop outs due to noncompliance and other reasons (7.5-10%). While 8-11% of participants may

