progress to diabetes yearly,^{72, 79, 80} all efforts will be made to retain these participants in the study and to include them in intent-to-treat analyses. The Power and effect size estimates for gait speed (SD=0.19) for α =0.05 for 60 participants and 53 participants per group are illustrated in the graph (Fig. 8) and based on our preliminary data in older women. The sample size of 60 participants per group will have 73% Power to detect a 0.09 m/s difference in gait speed. Within each group, 16 participants will be randomly selected and consented to undergo muscle biopsies at baseline and 6 months for secondary analyses of muscle histologic changes with metformin vs. placebo treatment. There is an expected change in these histologic measures within 6 months given prior studies that detect changes in AMPK activation, ATP concentration and insulin sensitivity prior to 6 months with use of metformin.^{3, 4} Estimated effect sizes of the difference in histologic measures between the two groups after 6 months are shown below in Table 3. While this study is adequately powered for 3 year outcomes in muscle loss, interim analyses may be performed by a Data Monitoring Committee (managed by the VA CSRD), given blinding of the primary investigator to the intervention, and the trial may be terminated early if a significant difference in the primary outcome between metformin- and placebo-treated groups is noted before 3 years.

	SD	70%	80%	90%
Capillary Density (AU)	0.35	0.32	0.36	0.42
IMCL (AU)	0.50	0.46	0.51	0.59
SDH (AU)	0.50	0.46	0.51	0.59
% Type I Fibers	24.0	21.8	24.6	28.4

Table 3 Estimated detectable difference in muscle histology measures at 80 and 90% Power

SD derived from measures in older insulin-resistant adults³⁶

Statistical Analyses

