To assess a difference in the primary outcomes of change in muscle mass and performance between metforminand placebo-treated groups, longitudinal (mixed effects) models will be used to estimate the trajectory of change. These models will account for correlation of outcomes within subjects and allows for those with missing followup data to be included in analyses. Four measures of muscle mass and performance (baseline, year 1, 2 and 3) are the outcomes in separate models. These will be modeled as a linear change over time, and other functional changes (squared, cubic and quadratic) will be evaluated. In the best fitting model, an interaction between time and group (metformin vs. placebo) will be included in the model to determine if changes in muscle mass/performance differ between the two groups. For the secondary outcomes of muscle histology, the discrete change in measures of mitochondrial content, muscle capillary density, percentage of fiber types and intramyocellular lipid content over 6 months will be calculated. The absolute and percentage changes in these measures will serve as the outcome in linear regression models with treatment group as the dichotomous exposure. Nonlinear associations between the exposure and outcomes will be evaluated with higher order terms. For the analyses of primary and secondary outcomes, potential confounders including demographic information, physical activity, diet, lifestyle factors, medical history and medication use are expected to be evenly distributed between the groups in a random fashion; nevertheless, we will evaluate for potential confounding by these factors and include them in multivariable models if they are significantly associated with our exposure and outcome and modify the effect size by >10%. There is no anticipated gender difference in the study outcomes, so the study has not been powered to detect a significant interaction by gender. However, the primary and secondary outcomes will also be stratified by gender to explore if there is a gender-specific muscle response to metformin. To account for missing data, multiple imputation modeling will constructed from participants with complete data. Participants with missing data will have those values imputed at each time point multiple imputation.⁸² Results will be reported with and without imputed values.

Data Integrity

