Potential benefits to participants include the detection and potentially earlier treatment of diabetes mellitus. Participants in both metformin and placebo groups will benefit from routine lifestyle modification counseling at yearly visits for prevention of diabetes.

Others may benefit from a greater understanding of the effect of metformin on muscle mass and function in insulin-resistant older adults.

VA Data Monitoring Committee (DMC)

A data monitoring committee will be provided by VA CSR&D. With DMC's experience in the conduct and monitoring of clinical trials, it will assist with ensuring the overall safety of study participants, assessing safety and efficacy of the study intervention, monitoring the overall conduct of the clinical trial including recommendations on recruitment and retention of participants and improvement of study drug adherence, and providing recommendations on stopping or continuation of the trial. SAEs and UPRs will be reported to the DMC. For further details, see the "Instructions for the Review of New (uninitiated) Protocols by DMC Members."

Inclusion of Women and Children

Because sarcopenia is a condition of older age, children will not be enrolled in this study. Women will be included in a proportion reflective of their gender distribution at the VAPORHCS.

Criteria for Discontinuation

Subjects will be withdrawn from further study drug administration in the event of any of the following:

• Diagnosis of diabetes

- If hospitalized for any reason and after 48 hours of discharge, there is evidence of renal dysfunction
- If they require contrast medium and after 48 hours of procedure, there is evidence of renal dysfunction
- Developed lactic acidosis
- Developed renal insufficiency at the level indicated by the FDA ($eGFR < 45 \text{ mL/min}/1.73 \text{ m}^2$).
- Development of B12 deficiency
- Excessive alcohol intake
- Subject withdraws consent
- Significant deviation from the protocol or eligibility criteria in the opinion of the investigator
- Any other reason that in the opinion of the investigator, would justify removing the subject from the study

There are no pre-defined stopping rules for termination of the study.

VA Research:

The following are the components of the study which will be conducted at the VAPORHCS:

- Advertising
- Recruitment
- Study visit activities at Screening, Baseline, half-yearly visits, and annual visits
 - Consent
 - Height, weight
 - o Blood pressure
 - Demographics
 - Medical history

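### The 80% power for lean mass assumes a realised 2.2-point difference, with no allowance for participants who stop study drug at diabetes diagnosis but stay in the intention-to-treat analysis

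*Combined protocol and SAP*

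**What the plan says.** All references are to the combined protocol and SAP.

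- **Effect and sample size** (Sample Size and Power). The basis is observational: "there was a significant difference (2.2%, p< 0.01) in the percentage change in appendicular lean mass over 3.5 years between metformin-treated and untreated men". With SD 4%, two-sided alpha 0.05 and an unpaired t-test, the plan derives 106 participants (53 per group) for 80% power.
- **Allowance** (same section). The plan randomises 120, 60 per group, "to allow for potential drop outs due to noncompliance and other reasons (7.5-10%). While 8-11% of participants may" progress to diabetes yearly. Of those who progress it says "all efforts will be made to retain these participants in the study and to include them in intent-to-treat analyses".
- **Stopping study drug.** Study Drug lists the reasons for discontinuation, among them "development of lactic acidosis; diagnosis of diabetes; hospitalization". Criteria for Discontinuation says "Subjects will be withdrawn from further study drug administration in the event of any of the following", and diagnosis of diabetes is the first item. Study Drug describes restarting only after hospitalisation, contrast medium or fasting procedures.
- **Analysis.** Statistical Analyses plans mixed models on four annual measurements, an approach that "allows for those with missing followup data to be included in analyses". Study Drug adds: "Compliance to study drug will be tracked and accounted for in analyses".
- **Claim.** Sample Size and Power concludes: "While this study is adequately powered for 3 year outcomes in muscle loss".

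**The concern.** Taken together, these statements mean that the plan expects to analyse metformin-arm participants who have been off metformin for one or two of the three years. The power calculation nevertheless uses the observed 2.2 points unreduced. At 8-11% a year, cumulative progression is 22-30% by year 3. The added headcount restores numbers lost to drop-out. It does nothing for people who are still measured but no longer treated.

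At stake is how a null or borderline lean-mass result would be read. Gait speed, the other sized primary outcome, is already put at 73% power for 60 per group, so the adequacy claim rests on lean mass. If the plan's own rules make the intention-to-treat difference smaller than 2.2 points, the claim is stronger than the design supports.

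**Working it through.** **Inputs from Sample Size and Power:** difference 2.2 points; SD 4%; two-sided alpha 0.05; 53 per group analysed; 60 per group randomised; drop-out 7.5-10%; progression to diabetes 8-11% a year. **From Labs and the Schedule of Study Procedures:** after baseline, fasting glucose is scheduled only at the annual visits.

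**1. The plan's own figure.** The standardised effect is 2.2/4 = 0.55. The non-central t calculation needs 52.9 per group, so 53; power at 53 is 80.1%. The stated 53 and 106 reproduce.

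**2. What the allowance covers.** 106/0.925 = 115 and 106/0.90 = 118, so 120 covers 7.5-10% loss of headcount. Starting from 60 per group, 60 × 0.90 = 54 and 60 × 0.925 = 55.5, so 54-55 complete. Undiluted power is 81-82% at 54-55 and 85% at 60.

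**3. Progression.** Cumulative over 3 years: 1 − 0.92³ = 22.1% and 1 − 0.89³ = 29.5%. Diagnosed by year 2, which is what matters for time off drug: 0.08 + 0.08 × 0.92 = 15.4% and 0.11 + 0.11 × 0.89 = 20.8%.

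**4. Dilution.** Assumptions: the effect accrues linearly on drug; there is no further gain after stopping; diagnosis falls at annual visits; rate r applies to the metformin arm; SD stays at 4%. Someone diagnosed at year 1 keeps 1/3 of the effect, at year 2 keeps 2/3, and at year 3 keeps all of it. The mean fraction kept is

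1 − (2/3)r − (1/3)r(1 − r) = [1 + (1 − r) + (1 − r)²]/3.

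- r = 0.08: (1 + 0.92 + 0.8464)/3 = 0.922; effect 2.2 × 0.922 = 2.03.
- r = 0.11: (1 + 0.89 + 0.7921)/3 = 0.894; effect 2.2 × 0.894 = 1.97.
- Half the quoted rate (an assumption), r = 0.04 and 0.055: 0.961 and 0.946; effects 2.11 and 2.08.

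**5. Mixed model, best case.** With visits at 0, 1, 2 and 3, Sxx = 5. If all variation in change is residual error σ², the variance of the fitted 3-year change is 9σ²/5 = 1.8σ², against 2σ² for the simple change score. The standard error ratio is √0.9 = 0.949. If all the variation is in the true individual slopes, the ratio is 1 and there is no gain. The best case divides the standardised effect by 0.949.

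**6. Power** (two-sided 0.05, non-central t; each range runs from the higher to the lower rate and across the sample sizes shown):

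| Metformin-arm stopping | Model | 54-55 per group | 60 per group |
|---|---|---|---|
| None (2.2 points realised) | t-test | 81-82% | 85% |
| 8-11% a year | t-test | 72-75% | 76-79% |
| 8-11% a year | mixed model, best case | 76-79% | 80-83% |
| 4-5.5% a year | t-test | 76-78% | 81-82% |
| 4-5.5% a year | mixed model, best case | 81-82% | 85-86% |

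**The case against.** **The calculation is right as stated.** True. The plan claims 80% power for a 2.2-point difference, and 53, 106 and 120 all reproduce. A reader might infer an error in the sample size arithmetic; there is none. What remains is an unstated condition, that the difference is actually realised.

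**The 2.2 points may already include some stopping.** This stands in part. The preliminary study grouped men by glycaemic status and treatment at baseline, and the protocol does not say that users stayed on metformin. To that extent the multiplier double-counts and the loss is smaller. Stopping triggered by a new diabetes diagnosis is a separate mechanism, so the concern remains.

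**The full rate may be too high for the metformin arm.** The 8-11% is quoted for participants overall, and Study Drug says this dose lowers diabetes risk. Applying the full rate to metformin is an assumption, as is halving it; hence both are shown.

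**The planned model is not a t-test and can use incomplete follow-up.** Effective numbers may therefore lie between 54-55 and 60, and precision may improve. At the favourable end this carries the figure past 80%. The protocol makes no power claim for this model.

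**The allowance mentions noncompliance, and compliance is to be accounted for.** Even if that word is read to cover some people off drug, 7.5-10% in total is well short of 22-30%. No method is given for the compliance analysis, and adjusting for compliance would not restore the power of an intention-to-treat comparison.

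**Stronger readings the documents do not support.** One could treat every progressor as losing the whole effect, but the protocol does not say benefit vanishes on stopping, and a diagnosis at the year 3 visit costs no time on drug. One could spread diagnoses through the year, but in-study glucose after baseline is measured only annually. One could also charge a loss for moving from 3.5 to 3 years, but the time base of the 4% SD is not given, so no figure can be put on it.

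**Conclusion.** The point holds as a minor one about a power assumption that the design does not meet. The 80% is valid for a realised 2.2-point difference. Under the plan's own stopping rule, quoted incidence and intention-to-treat retention, the expected difference is about 2.0 points under the step 4 assumptions, and the t-test used for sizing falls short of 80% across 54-60 per group.

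A reader might infer that the trial is clearly underpowered. The documents do not support that: lower metformin-arm incidence, follow-up close to 60 per group, or a gain from the mixed model can each narrow or close the gap. The omission is certain; its size is not. Treatment after diagnosis is unspecified and could move the loss either way.

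**What to change.** In Sample Size and Power:

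1. Keep the 106 calculation, described as power for a realised 2.2-point difference.
2. Add lean-mass power for the 3-year intention-to-treat difference as a range: about 72-79% by t-test at the quoted incidence for 54-60 per group, higher with lower metformin-arm incidence or a mixed-model gain.
3. List the assumptions: effect linear in time on drug, no further gain after stopping, diagnosis at annual visits, the yearly stopping rate in the metformin arm (quoted rate and a lower case), and t-test or mixed model. Note that the observational 2.2 points may already include some stopping.
4. Limit the statement that the study is adequately powered for 3-year muscle loss to a realised 2.2-point difference.

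The cost is protocol wording only. Sample size, analysis and the rule for stopping study drug are unchanged; the plan gives up a single 80% figure for a range.

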Initial contact with potential subjects will occur in clinic, by phone or by mail. If in clinic, their provider will approach them first to see if they are interested in the study and ask if they agree to be contacted by study personnel. If the patient agrees, they can initiate contact with the study team by phone or have the study coordinator speak to them in clinic or call them later. If initial contact is by phone, potential subjects can contact the study coordinator directly using information on the advertising flyers. If initial contact is by mail, potential subjects will receive a recruitment letter indicating the option to opt out by returning an included letter indicating the wish to not be contacted again. The letter will state that if a response is not received within two weeks, potential subjects may be contacted by phone. Included with this mailing will be an approved informational letter from the Chief of Primary Care.

During the screening telephone call, a study coordinator will discuss the inclusion and exclusion criteria and provide further details on the study. If participants are interested and are potentially eligible, a Screening visit will be scheduled.

Study design

The proposed study duration of 3 years has been selected based on our prior observational findings over 3.5 years.²⁵ Eligible participants will have an initial Baseline visit, followed by randomization to placebo or metformin (Fig. 7). Between visits, telephone surveying of medication compliance will be obtained and any AEs reviewed. Participants will be seen every 6 months, and have annual study visits for measurements of muscle mass and performance. A substudy of participants will also include muscle biopsies at 2 visits; within 14 days from baseline and at the 6 month visit.

9

Primary outcome measures

To test the primary hypothesis that metformin-treated participants will have a slower decline in muscle mass and physical performance than those on placebo, we will be measuring total and appendicular lean mass using dual x-ray absorptiometry and assessing physical performance with the short physical performance battery (SPPB), grip strength and a 400 meter walk. Our preliminary findings suggest that there should be attenuation in the loss in appendicular lean mass and gait speed, and additional performance measures will be explored.

Secondary outcome measures

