The secondary hypothesis is that the muscle composition of metformin-treated participants will have a greater increase in number of oxidative fibers, decrease in intramyocellular lipid, increase in capillary density and increase in the number of mitochondria than placebo-treated participants. These outcomes have been chosen based on our hypothetical framework in Figure 1 that was developed from known alterations in these measures in animal models treated with metformin or other AMPK agonists. Quantification of intramyocellular lipid, fiber types, capillary density and mitochondrial content will be obtained through histochemical analyses of muscle biopsy specimens as described in the Muscle Biopsy section.

Study Visits

All visits will be completed at VAPORHCS and/or at OHSU.

Screening Visit

IRB-approved study personnel will have a full discussion with the potential subject, including information on study visits, procedures, risks, and benefits. All participants will be informed of their right to withdraw from the study at any time. The principal investigator will answer any questions from participants at any time. Participants will provide written informed consent prior to any study procedures being performed. A copy of the IRB-approved informed consent and signed HIPAA authorization form will be given to the subject. Demographic information (including age, gender, and race) and lifestyle factors (including physical activity, smoking history and alcohol intake) will be obtained. Medical history (including self-reported physician medical diagnoses), drug allergies/adverse effects and medications will be obtained. Height, weight and blood pressure (BP) will be measured. Criteria for exclusion criteria will be formally reviewed. Participants must demonstrate that they are able to ambulate 400 meters without assistance. Laboratory assessment for B12 levels and liver, kidney and clotting function will be performed. The total amount of blood drawn will be 10 ml. Labs will be drawn for fasting glucose to identify participants with IFG. All labs will be ordered after consent is obtained. Participants will be instructed to remain fasting for 12 hours prior to the study day. This visit could take up to 2 hours. Participants who have IFG will be scheduled to attend a Baseline visit if the Screening visit does not reveal presence of an exclusion criterion.

Baseline Visit

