The Baseline visit will occur in 14 days (+/- 7 days) from Screening. Participants will be instructed to remain fasting for 12 hours prior to the study day. This visit could take up to 3 hours. The study measures will be conducted by the IRB-approved study team who are all blinded to treatment allocation. The participants will first get a fasting blood draw at VAPORHCS. All study subjects will be provided breakfast after their fasting lab draw has been done. A fasting glucose level will be measured. Subjects will proceed with the following study measures: review and completion of questionnaires, medication inventory, physical performance tests, and whole body DXA. For those subjects who signed the consent indicating their interest in participating in the muscle biopsy substudy and are eligible, they will be scheduled for a Baseline muscle biopsy visit within 14 days of their

baseline visit.

Because adults with IFG have a higher risk of developing type 2 diabetes, all study participants will receive guidelines for diet and lifestyle modification consistent with the goals of the Diabetes Prevention Program at baseline and yearly visits.⁷² These include intake of < 25% of calories as fat and engaging in ≥ 150 minutes of physical activity weekly.

Baseline Muscle Biopsy Visit (if in substudy)

Participants enrolled in the muscle biopsy substudy will receive a telephone call within 3 days prior to their biopsy visits to remind them to fast for 12 hours prior to the visit, to remind them to abstain from vigorous physical activity, and to ensure they are not on anticoagulant or antiplatelet medications within 7 days from the biopsy visit with the exception of aspirin or other anti-inflammatory medications which cannot be taken within 3 days of the biopsy visit.

This visit will occur within 14 days from Baseline, and it could take up to 3 hours. It will be completed at OHSU. Eligibility criteria for the muscle biopsy will again be reviewed, and if there are no contraindications, the participant will undergo muscle biopsy. Participants will be given breakfast after muscle biopsy has been obtained.

Phone calls between visits

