We have chosen to study metformin in this clinical trial due to the observation that metformin use was associated with an attenuated loss of muscle mass and function in our preliminary studies. While both metformin and thiazolidinediones can upregulate AMPK and PGC1a in muscle to increase muscle fatty acid oxidation, angiogenesis, mitochondrial biogenesis and oxidative muscle fibers for healthier-appearing muscle,^{32, 34, 68} metformin has additional benefits on mortality, microvascular and macrovascular outcomes in patients with type 2 diabetes;⁶⁹ whereas, thiazolidinediones have associated risks of adverse cardiovascular outcomes.^{70, 71}

The VA Research Pharmacy will be used to randomize, dispense, and track blinded placebo and metformin tablets in 3-month supplies. A covariate-adaptive randomization scheme will be used to ensure equal age, gender and race distributions. The investigators and study participants will be blinded to the randomization of the study drug assignments. A 90-day supply of study drug will be mailed every 3 months to participants with a pre-paid envelope for returning unused study drugs for pill counts. An additional 4-day buffer may be included to avoid lapses in study drug administration due to unforeseen complications in medication delivery and/or receipt. To minimize self-limiting gastrointestinal side effects, participants randomized to metformin will begin with an oral dose of 850 mg tablets once daily (taken with meals) for 1 month with titration up to 850 mg twice daily for the remainder of the study. We anticipate an effect on muscle using this dosage, since a significant reduction in peripheral insulin resistance occurs even with a metformin daily dosage of 750 mg.⁶¹ Furthermore, this dose was safe and effective in lowering the risk of diabetes for subjects with prediabetes in the Diabetes Prevention Program.⁷⁵ Plans for monitoring and preventing risks associated with metformin are further discussed under Human Subjects.

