Imaging (DXA): DXAs will occur at OHSU. At Baseline and the annual visits, whole body scans will be taken with a Hologic QDR 4500W DXA scanner by a certified DXA operator to determine total body lean mass and appendicular lean mass (kilograms), as previously described.^{59, 60} Standard Hologic procedures will be used to define regions on the whole body DXA scans using cut lines. The arms will be delineated by a cut line drawn between the head of the humerus and the scapula at the glenoid fossa and the leg will be delineated by a cut line drawn across the midpoint of the femoral neck. Appendicular lean mass will be calculated as the sum of lean mass in the arms and legs. Hologic whole-body QC phantoms will be scanned daily to monitor longitudinal changes so that correction factors can be applied to measurements to adjust for longitudinal drift.

Muscle Biopsy studies (for those in the substudy): Subjects are asked to participate in the muscle biopsy studies based on their platelet and INR results. There will be 32 subjects in the substudy. Subjects will not enroll in the muscle biopsy studies or have a second muscle biopsy if they take medications that increase bleeding risk, have an allergy to lidocaine, or have platelet count < 150 billion/L, INR > 1.2, or aPTT > 36 seconds.

At the Baseline Muscle Biopsy visit and 6 month visit, fasting muscle biopsy samples will be obtained at OHSU by a physician or certified nurse practitioner from the vastus lateralis muscle, 15 cm above the patella using the modified Bergstrom technique, as described.^{36, 74-76} Using a 2% lidocaine for anesthetic, a small, ¹/₄ incision will be made in the skin and fascia to place a 5 mm Bergstrom biopsy needle while suction is applied through the 140 cc syringe, obtaining approximately 150-200 mg of muscle. The incision will be closed with sterile adhesive strips, and a pressure bandage will be applied for a period of 24 hours. This procedure takes approximately 15 minutes, is a relatively painless, and well-tolerated in older adults. Subjects will be instructed not to perform physical exercise 48 hours prior to the muscle biopsy procedure to help prevent acute effects of exercise on intramyocellular lipids (IMCL) (7:8). They will also be given discharge instructions after the procedure for precautions to follow to prevent complications.

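### The biopsy substudy is selected in two incompatible ways, and under the volunteer route the 16:16 split behind Table 3 is left to chance

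*Combined protocol and SAP*

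**What the plan says.** Two selection procedures appear in the combined protocol and SAP.

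- **Within-arm draw.** Statistical considerations, Sample Size and Power: "Within each group, 16 participants will be randomly selected and consented to undergo muscle biopsies at baseline and 6 months". Read literally, selection and consent happen inside treatment groups, so the assignment must be known to whoever selects.
- **Volunteers.** Baseline Visit: "For those subjects who signed the consent indicating their interest in participating in the muscle biopsy substudy and are eligible, they will be scheduled"; the appointment meant is the first biopsy. Muscle Biopsy studies: "Subjects are asked to participate in the muscle biopsy studies based on their platelet and INR results", and "There will be 32 subjects in the substudy". Study Population likewise treats those meeting the extra criteria as candidates. None of these places mentions a random draw or an arm quota.

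On timing, the Screening Visit takes consent and states "Laboratory assessment for B12 levels and liver, kidney and clotting function will be performed". Study design states "Eligible participants will have an initial Baseline visit, followed by randomization to placebo or metformin". Interest in biopsy and clotting eligibility can therefore be known before randomization, although this is inferred from the order of visits and no single sentence says it.

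On allocation, Study Drug states "A covariate-adaptive randomization scheme will be used to ensure equal age, gender and race distributions". Substudy status is not listed. Investigators and participants are blinded, the Baseline Visit describes the study team as blinded, and the research pharmacy's listed tasks do not include drawing a biopsy sample.

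**The concern.** All the histology outcomes, and with them the secondary hypothesis, rest on 32 people. The within-arm rule would fix 16 per arm, but it uses allocation to decide who is biopsied and names nobody to make the draw. The volunteer rule can be run by a blinded team, but nothing in it delivers the 16 per arm that Table 3 assumes. It also does nothing to balance age, gender and race inside the substudy, since balance over 120 does not carry over to a subset of 32. A reader of the results could not tell from the plan which rule had been used or whether allocation played a part in selection.

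**Working it through.** **1. Reproduce Table 3.** Inputs: 16 per arm and the SDs in Table 3. Two-sided α = 0.05 and an unpaired t-test are stated for the primary outcome and assumed here, because Table 3 states neither. Power is that of a noncentral t with n₁+n₂−2 degrees of freedom and noncentrality Δ / (SD·√(1/n₁+1/n₂)).

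| Measure | SD | Table 3 at 70/80/90% | Recomputed, 16 vs 16 |
|---|---|---|---|
| Capillary density | 0.35 | 0.32 / 0.36 / 0.42 | 0.318 / 0.358 / 0.415 |
| IMCL, SDH | 0.50 | 0.46 / 0.51 / 0.59 | 0.454 / 0.512 / 0.592 |
| % Type I fibers | 24.0 | 21.8 / 24.6 / 28.4 | 21.78 / 24.57 / 28.43 |

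The table matches to rounding, so it does rest on 16:16.

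**2. Chance of that split under the volunteer route.** If substudy status plays no part in allocation and the arms finish 60:60, the number of the 32 on metformin follows P(k) = C(60,k)·C(60,32−k)/C(120,32).

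- Exactly 16:16: 16.3%
- 13:19 or worse: 30.2%
- 12:20 or worse: 14.8%

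With Binomial(32, 0.5) instead, these are 14.0%, 37.7% and 21.5%.

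**3. Power cost.** For IMCL at Δ = 0.51, SD = 0.50:

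| Split | √(1/n₁+1/n₂) | Noncentrality | Power |
|---|---|---|---|
| 16:16 | 0.3536 | 2.885 | 79.7% |
| 14:18 | 0.3564 | 2.862 | 79.1% |
| 13:19 | 0.3599 | 2.834 | 78.3% |
| 12:20 | 0.3651 | 2.793 | 77.1% |

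Averaged over all splits, power is 78.8% (hypergeometric) or 78.4% (binomial), a loss of about 1 point. For comparison, lost second biopsies cost more: 76.9% at 15 per arm and 73.8% at 14 per arm.

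**4. Covariate balance inside the substudy.** Take a factor carried by 16 of the 32, with a 16:16 split. A gap of 25 points or more means 6 or fewer, or 10 or more, carriers in one arm. Hypergeometric(32, 16, 16) gives 1 − 0.276 − 2(0.218) ≈ 29%. That figure ignores the trial-wide balancing. Simulating the adaptive scheme brings it to about 12% for the age group. Assumptions: 120 participants, 32 of them in the substudy at random, biased-coin probability 0.8, a 50% age factor, 10% women and 15% minority race. Setting all three factors at 50% gives much the same result.

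**5. Which remedy works, in the same simulation.**

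| Scheme | 13:19 or worse | Age-group gap ≥ 25 points in substudy |
|---|---|---|
| As planned | about 30% | about 12% |
| Membership added as one more marginal factor | 2% or less | 12–13% |
| Scheme run separately for members and non-members | about 0.2% | 1–2% |

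A marginal factor evens out the number of members per arm, not the covariates among them. Running the scheme separately within each membership level does both.

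**The case against.** The strongest reply is that little follows from this. A 1-point average loss of power on a secondary outcome is trivial, and missed second biopsies matter more. That stands.

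A reader might infer that the histology comparison is biased or the blind broken. The documents do not support this. If selection does not depend on knowledge of the assignment, either route gives an unbiased comparison in expectation. The pharmacy holds the allocation and could draw 16 per arm from consenting, eligible people without unblinding anyone else; the gap is that the plan gives nobody that task.

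A reader might also infer severe covariate imbalance from the 29% figure. That figure leaves out the plan's own trial-wide balancing, counts gaps of exactly 25 points on a scale that moves in 12.5-point steps, and needs a factor carried by half the substudy. For gender it could be far smaller: women are enrolled in proportion to the site's population, for which no figure is given.

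The outcomes are within-person changes, which removes fixed differences in level. Statistical Analyses also allows covariate adjustment, but only if a factor is significantly associated with exposure and outcome and shifts the effect by more than 10%. That is a data-driven rule with little force at n = 32.

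Finally, membership before randomization is provisional. Eligibility is reviewed again at the Baseline Muscle Biopsy Visit, up to 14 days after Baseline, and no passage places that visit before randomization or first dose. This limits the remedy but does not defeat it.

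None of these replies settles which selection rule applies, who applies it, or when.

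**Conclusion.** The concern holds as a modest matter of consistency and precision for the secondary histology outcomes. The two selection rules conflict, and under the volunteer rule 16:16 is left to chance: about 16% for an exact split and about 30% for 13:19 or worse, assuming a final 60:60 allocation. The average power loss is about 1 point, with 77% at 12:20. An age-group gap of 25 points or more within the substudy has about a 12% chance, which rests on the assumed factor prevalences and biased-coin probability because the documents give neither. No bias is shown, and the primary outcomes are unaffected. It is worth correcting because the remedy is nearly free.

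**What to change.** Reconcile Study Population, Baseline Visit, Muscle Biopsy studies, and Sample Size and Power around one rule:

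1. Substudy members are those who consent to biopsy and meet the substudy criteria before randomization, until 32 are reached. Remove the statement that people are drawn at random within each treatment group.
2. The research pharmacy stratifies the covariate-adaptive randomization by substudy membership, running the age, gender and race scheme separately for members and non-members. Adding membership as one more marginal factor is not enough.
3. Histology is analysed by membership as set at randomization. Members who later fail the recheck or miss a biopsy are reported as such.
4. State where the baseline biopsy falls relative to randomization.

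**Cost.** One setting in the randomization program and a few sentences of protocol text, with no added visits or staff. Overall balance across the 120 becomes very slightly looser. Membership stays provisional until the recheck at the biopsy visit, so the evaluable split may still drift a little from 16:16. The change can apply only to participants not yet randomized.
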